5.2. Exclusion Criteria

Patients meeting any of the following criteria will be excluded from the study:

1. Received an investigational anticancer drug within 4 weeks of the first planned SL-901 dose.
2. Received major surgery, radiotherapy, or immunotherapy within 4 weeks of C1D1. Localized palliative radiotherapy is permitted for symptom control.
3. Received chemotherapy regimens with delayed toxicity within 4 weeks (6 weeks for prior nitrosourea or mitomycin C) of C1D1.
4. Received chemotherapy regimens given continuously or on a weekly basis which have limited potential for delayed toxicity within 2 weeks of C1D1.

5. Clinically significant, unresolved toxicity from previous anticancer therapy \geq Grade 2 (except alopecia), as determined by the Investigator using the National Cancer Institute Common Terminology Criteria for Adverse Events (NCI CTCAE), version 5.0.
6. Presence of active gastrointestinal disease or other condition that will interfere significantly with the absorption, distribution, metabolism, or excretion of drugs.
7. Left ventricular ejection fraction $<50\%$.
8. Corrected QT interval (based on Fridericia's formula) >450 msec.
9. Type 1 or 2 diabetes mellitus requiring medication. (In Part 1b, patients with type 2 diabetes mellitus controlled by medication, as indicated by a glycated hemoglobin of $\leq 7.5\%$ are eligible.)
10. Known active human immunodeficiency virus, hepatitis B, or hepatitis C infection.
11. Ongoing systemic bacterial, fungal, or viral infection.
12. History of interstitial pneumonitis.
13. Absolute neutrophil count (ANC) $<1.5 \times 10^9/L$.
14. Hemoglobin <10 g/dL.
15. Aspartate aminotransferase (AST) or alanine aminotransferase (ALT) $>2.5 \times$ the upper limit of normal (ULN).
16. Known hypersensitivity or allergy to the active ingredient or excipients of SL-901.
17. Breast-feeding females.

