- 6) If a woman of childbearing potential (WOCBP), the patient has a negative serum or urine pregnancy test within 1 week before Cycle 1, Day 1 (C1D1). Refer to Section 8.1.3 for further practical information about contraception.
- 7) The patient (either male or female) agrees to use acceptable contraceptive methods for the duration of time in the study, and to continue to use acceptable contraceptive methods for 1 month after the last dose of SL-901. Refer to Section 8.1.3 for further practical information about contraception.
- 8) Able to provide written informed consent.
- 9) Willing to provide consent for biomarker analysis of (existing paraffin-embedded) tumor samples.

Patients meeting any of the following criteria will be excluded from the study:

- 1) Received an investigational anticancer drug within 4 weeks of the first planned SL-901 dose.
- 2) Received major surgery, radiotherapy, or immunotherapy within 4 weeks of C1D1. Localized palliative radiotherapy is permitted for symptom control.
- 3) Received chemotherapy regimens with delayed toxicity within 4 weeks (6 weeks for prior nitrosourea or mitomycin C) of C1D1.
- 4) Received chemotherapy regimens given continuously or on a weekly basis which have limited potential for delayed toxicity within 2 weeks of C1D1.
- 5) Clinically significant, unresolved toxicity from previous anticancer therapy \geq Grade 2 (except alopecia), as determined by the Investigator using the National Cancer Institute Common Terminology Criteria for Adverse Events (NCI CTCAE), version 5.0.
- 6) Presence of active gastrointestinal disease or other condition that will interfere significantly with the absorption, distribution, metabolism, or excretion of drugs.
- 7) Left ventricular ejection fraction $<50\%$.
- 8) Corrected QT interval (based on Fridericia's formula) >450 msec.
- 9) Type 1 or 2 diabetes mellitus requiring medication. (In Part 1b, patients with type 2 diabetes mellitus controlled by medication, as indicated by a glycated hemoglobin of $\leq 7.5\%$ are eligible.)
- 10) Known active human immunodeficiency virus, hepatitis B, or hepatitis C infection.
- 11) Ongoing systemic bacterial, fungal, or viral infection.
- 12) History of interstitial pneumonitis.
- 13) Absolute neutrophil count (ANC) $<1.5 \times 10^9/L$.
- 14) Hemoglobin <10 g/dL.
- 15) Aspartate aminotransferase (AST) or alanine aminotransferase (ALT) $>2.5 \times$ the upper limit of normal (ULN).

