6.4. SL-901 Dose and Administration

In both study parts, for the purposes of this study, a treatment cycle is considered to be 28 days, with daily dosing throughout the cycle.

Each SL-901 dose will be self-administered by the patient without food, either 2 hours before or 2 hours after food. The dose regimen is dependent on the patient's cohort assignment (see [Table 5](#)), and SL-901 doses should be administered at approximately the same time of day on each day of the cycle, if possible. For patients on the BID schedule, doses should be taken morning and evening at approximately the same time each day of the cycle, if possible.

On PK sample collection days, SL-901 should be administered at the study center and should be administered at (approximately) the same time of day on each day of the cycle, if possible. For patients on the BID schedule, start of PK collection must occur before the first dose of the day.

In Part 1a, the SL-901 starting dose is 20 mg on a QD schedule and a total daily dose of 40 mg on a BID schedule, as specified in [Table 5](#). The QD and BID schedules will be tested in parallel, with enrollment to the current cohort for each schedule conducted on an every other patient basis.

In Part 1b, the regimen of SL-901 will be based on the clinical experience in Part 1a.

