8. STUDY ASSESSMENTS

8.1. Screening Assessments

Screening assessments are performed subsequent to the patient providing an informed consent and before the first administration of SL-901 at the Run-in PK sampling day, see [Section 8.7](#). These assessments are to be performed within 28 days of the Run-in PK sampling day (during Screening), unless otherwise specified.

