5.2. Schematic study design

Screening assessments are performed subsequent to the patient providing an informed consent and within 28 days before the first administration of SL-901 at the Run-in PK sampling day, unless otherwise specified.

In both study parts a treatment cycle is considered to be 28 days, with daily dosing throughout the cycle.

All patients will receive SL-901 as a single agent in an open-label fashion; study drug will be dispensed to patients at scheduled study center visits on a per-cycle basis. SL-901 capsules (20 mg and 60 mg) are packaged into 50-cc high-density polyethylene (HDPE) bottles, 14 capsules per bottle.

Tumor assessment will occur at Screening (for identification of baseline disease) and every 2 cycles of treatment thereafter. Response will be evaluated using Response Evaluation Criteria in Solid Tumors (RECIST) v1.1.

[figure not shown]
In Part 1a, a serially sampled PK profile will be obtained for a single dose (Run-in PK sampling) and at steady-state (C1D15); in Part 1b, the PK sample collection schedule will be informed by data collected in Part 1a.

[figure not shown]
All Serious Adverse Events (SAEs) and non-SAEs will be recorded in the study's clinical database from the day of informed consent signature (SAEs) or from the day of first exposure to SL-901 (AEs) through 30 days after the last dose of SL-901.

[figure not shown]
After completion of the End of Treatment (EOT) visit, patients will then be followed every 90 days for survival status for 12 months. The survival follow-up may be by telephone contact. If the patient discontinued study drug for reasons other than progressive disease, disease assessments should continue to be performed on an every 8-week basis (± 1 week) through 6 months after the first study drug dose and then on an every 90-day basis or until, in the judgment of the Investigator, there is evidence of relapsed or progressive disease.

[figure not shown]

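### In Part 1a, exclusions 2–4 count washout to C1D1, so the run-in dose, which opens the DLT window, can be given 3–7 days before that washout has elapsed

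*Protocol*

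**What the plan says.** Adjacent exclusion criteria in Protocol Section 5.2, repeated in the synopsis (Section 1.1), use two different anchors.

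- Exclusion 1 counts to first exposure: "Received an investigational anticancer drug within 4 weeks of the first planned SL-901 dose".
- Exclusion 2 counts to C1D1: "Received major surgery, radiotherapy, or immunotherapy within 4 weeks of C1D1". Localized palliative radiotherapy is exempt.
- Exclusion 3 counts to C1D1: "Received chemotherapy regimens with delayed toxicity within 4 weeks (6 weeks for prior nitrosourea or mitomycin C) of C1D1".
- Exclusion 4 covers continuous or weekly regimens "which have limited potential for delayed toxicity within 2 weeks of C1D1".

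In Part 1a, C1D1 is not the day of first exposure. Protocol Section 8.1 places screening "before the first administration of SL-901 at the Run-in PK sampling day". SAP Section 5.2 describes the run-in as a single dose, and Protocol Table 8 puts it 3–7 days before C1D1, in Part 1a only. Daily dosing belongs to the cycle: "a treatment cycle is considered to be 28 days, with daily dosing throughout the cycle" (Protocol Section 6.4).

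Protocol Section 6.4.2 counts DLTs from the run-in PK period through C1. SAP Section 3.1 confirms this, and SAP Section 7.3 makes the complete run-in dose a condition of DLT evaluability, except for patients who discontinue Cycle 1 because of a DLT.

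**The concern.** A washout should be complete before first exposure, so that toxicity seen afterwards can be attributed to the study drug. Here the first exposure and the start of DLT observation both precede the day to which exclusions 2–4 count.

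A toxicity of earlier treatment that first appears between the run-in dose and C1D1 could be scored as a DLT. Cohorts are small, so single events matter. Under Protocol Section 6.4.1, one DLT in three patients adds up to three more patients. Two or more end escalation on that schedule and make the previous lower dose level the MTD. Such an event would also be treatment-emergent by timing alone (Protocol Section 9.3.4) and so enter the TEAE tables, which belong to the primary safety endpoint.

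**Working it through.** The plan gives no figure of its own on this point, so the check is date arithmetic.

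**Inputs**
- Washout W to C1D1 (Protocol Section 5.2): 28 days (exclusions 2 and 3), 42 days (exclusion 3, nitrosourea or mitomycin C), 14 days (exclusion 4).
- Run-in lead time L (Protocol Table 8): 3 to 7 days.
- Cycle length: 28 days of daily dosing (Protocol Section 6.4).
- Convention: therapy exactly W days before C1D1 is taken as permitted.

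**Shortest permitted interval from last prior therapy to first SL-901 dose = W − L**

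| Criterion | W | L = 3 | L = 7 | Shortfall, L/W |
|---|---|---|---|---|
| Exclusions 2, 3 | 28 | 25 | 21 | 3/28 = 10.7% to 7/28 = 25.0% |
| Exclusion 3, nitrosourea or mitomycin C | 42 | 39 | 35 | 3/42 = 7.1% to 7/42 = 16.7% |
| Exclusion 4 | 14 | 11 | 7 | 3/14 = 21.4% to 7/14 = 50.0% |

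These are worst cases, for a patient exactly at the limit. Someone whose last therapy was at least W + L days before C1D1 is unaffected.

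**Doses given before the washout has elapsed**
- QD: 1 run-in + 28 in C1 = 29 planned doses; 1/29 = 3.4%.
- BID: 1 run-in + 56 in C1 = 57 planned doses; 1/57 = 1.8%.

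**Share of the DLT window before C1D1 = L/(L + 28)**
- L = 3: 3/31 = 9.7%, leaving 28/31 = 90.3% after the washout.
- L = 7: 7/35 = 20.0%, leaving 28/35 = 80.0%.

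These shares are calendar time for a patient at the limit. They are not probabilities of misattribution.

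**After re-anchoring to the first dose**

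The minimum before first exposure becomes the full 28, 42 or 14 days. C1D1 then falls at least W + L days after prior therapy: 31–35, 45–49 or 17–21 days.

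**Do other provisions close the gap?**
- Exclusion 5 ("Clinically significant, unresolved toxicity from previous anticancer therapy" of Grade 2 or higher) and exclusions 13–15 (ANC, hemoglobin, AST/ALT) screen for toxicity already present. Exclusion 3 is concerned with toxicity that appears late.
- Section 5.2 sets no platelet threshold, although thrombocytopenia can be a DLT.
- For pregnancy testing, inclusion 6 also refers to C1D1, but Protocol Section 8.1.3 adds a test that must be negative before the run-in dose. The visible text has no equivalent for exclusions 2–4.

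**The case against.** The strongest reply is that no rule is broken. Exclusions 2–4 define their own endpoint, and C1D1 is a defensible one because repeated dosing starts there and the run-in is one dose taken for PK. A stricter anchor for investigational agents, whose toxicity may be less well known, could be deliberate. Nothing in the documents shows that 28 days is adequate and 21–25 is not, and late effects can still appear after any cut-off.

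Harm also needs several things together: a patient near the limit, a late toxicity first appearing in a window of 3–7 days, severity at DLT level, and attribution to SL-901. Protocol Section 8.2.2 tells the investigator to weigh other explanations, and a review committee makes the escalation decisions. One false DLT only expands a cohort; stopping a schedule takes a second. The largest relative shortfall concerns regimens chosen for limited delayed toxicity. The schedule of assessments is not visible, so repeat eligibility checks at the run-in cannot be excluded. Finally, the study was stopped early.

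Most of this stands as a limit on size. It does not remove the mismatch. No reason is given for two anchors in adjacent criteria. The causality requirement is also asymmetric: under Protocol Section 6.4.2 the Sponsor may override an unrelated assessment but may not reverse a related one, and Section 8.2.2 counts possibly related events as related. SAP Section 7.2.2 allows that category even where other drugs could explain the event. A late effect of recent chemotherapy could fit there.

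**Conclusion.** The concern holds, as a minor point. For a Part 1a patient at the limit of exclusions 2–4, first exposure and DLT observation can begin 3–7 days before the stated washout has elapsed. One dose is affected, and 80.0%–90.3% of the DLT window falls after the washout.

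The timing follows directly from the documents. The consequence for DLT counts is a possibility whose frequency cannot be estimated: neither document gives the number of patients near the limit or a rate of late toxicity. That the anchor was simply not updated for the run-in is an inference. Part 1b is unaffected, because Table 8 gives it no run-in and SAP Section 4 records that it was not started.

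**What to change.** In exclusions 2, 3 and 4, in both the synopsis and Protocol Section 5.2, count the washout to the first planned SL-901 dose instead of C1D1, using the wording of exclusion 1. Durations stay the same, and Part 1b needs no separate text because its first dose has no run-in before it.

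The cost is a protocol amendment changing three criteria in two places, and a delay of at most 3–7 days for some Part 1a patients. Because the study was stopped early, the gain is confined to any Part 1a enrollment after the change, or to a later protocol that reuses these criteria.

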5.3. Screen Failures

Screen failures are defined as patients who consent to participate in the clinical trial but are not subsequently treated with SL-901. A minimal set of screen failure information is required to ensure transparent reporting of screen failure patients, to meet the Consolidated Standards of Reporting Trials (CONSORT) publishing requirements and to respond to queries from regulatory authorities. The required information includes demography, screen failure details, eligibility criteria, and any SAE experienced.

Individuals who do not meet the criteria for participation in this trial (screen failure) may be rescreened once. Rescreened patients will be assigned a new patient number (different from the initial Screening number).

5.4. Source of Patients

This will be a multi-center study. Each study center is required to obtain local Institutional Review Board (IRB)/Ethics Committee (EC) and national regulatory approval to conduct the study before enrollment of patients may commence. Patients meeting the entrance criteria who are known or referred to the study center will be eligible for enrollment.

6. STUDY DRUG

6.1. Study Drug Supply

All patients participating in this study will receive SL-901 as a single agent in an open-label fashion. The Sponsor will supply SL-901 to all clinical sites.

6.2. Study Drug Packaging and Storage

SL-901 capsules (20 mg and 60 mg) are packaged into 50-cc high-density polyethylene (HDPE) bottles, 14 capsules per bottle. Bottles are capped with a child resistant tamper evident polypropylene closure.

All bottles are labeled with a single panel clinical label containing pertinent information for drug receipt and handling. Labeled bottles of 20 mg and 60 mg SL-901 capsules received from the distributor should be stored in a locked cabinet accessible only to appropriate study personnel.

SL-901 capsules are not to be stored above 25°C or frozen and are to be stored protected from light. Keep out of reach of children. For additional information on study drug handling including dispensing directions refer to the SL-901 Pharmacy Manual.

6.3. Study Drug Accountability

Study drug will be dispensed to patients at scheduled study center visits on a per-cycle basis. The Investigator or designee will maintain accurate records of receipt and condition of the study drug, including dates of receipt and temperature monitoring. In addition, records will be kept of the date dispensed, quantity dispensed, and the patient to whom study drug was dispensed. Any reasons for departure from the protocol-specified dispensing regimen must also be recorded in source documents and in the electronic case report form (eCRF).

The Investigator or designee is responsible for the accountability of all used and unused study drug containers and unused study drug. The site identification number and patient identification number are to be recorded on each study drug accountability log. Each time study personnel dispenses study drug for a patient, he or she is to record the date dispensed, number of capsules of study drug dispensed, and his or her initials. When the patient returns study drug, study personnel are to record the date returned, the number of capsules returned or empty bottle(s), and any comments. Study personnel are to monitor the inventory of clinical supplies and maintain a count of all used and unused containers. The Clinical Research Associate (CRA) will review study drug accountability records during routine monitoring visits. At the completion of the study, there will be a final reconciliation of all study drug.

6.4. SL-901 Dose and Administration

In both study parts, for the purposes of this study, a treatment cycle is considered to be 28 days, with daily dosing throughout the cycle.

Each SL-901 dose will be self-administered by the patient without food, either 2 hours before or 2 hours after food. The dose regimen is dependent on the patient's cohort assignment (see [Table 5](#)), and SL-901 doses should be administered at approximately the same time of day on each day of the cycle, if possible. For patients on the BID schedule, doses should be taken morning and evening at approximately the same time each day of the cycle, if possible.

On PK sample collection days, SL-901 should be administered at the study center and should be administered at (approximately) the same time of day on each day of the cycle, if possible. For patients on the BID schedule, start of PK collection must occur before the first dose of the day.

In Part 1a, the SL-901 starting dose is 20 mg on a QD schedule and a total daily dose of 40 mg on a BID schedule, as specified in [Table 5](#). The QD and BID schedules will be tested in parallel, with enrollment to the current cohort for each schedule conducted on an every other patient basis.

In Part 1b, the regimen of SL-901 will be based on the clinical experience in Part 1a.

6.4.1. Dose-Escalation Scheme in Part 1a

Initially, up to 3 patients are to be enrolled in each cohort. After 3 patients complete C1 and have safety evaluations performed through C2D1, and if:

- None of these 3 patients experience a DLT in either dosing schedule, then enrollment of the next cohort may commence.
- 1 of 3 patients within a cohort experiences a DLT, then up to 3 additional patients are to be enrolled sequentially at that dose level in that dosing schedule. If none of the additional 3 patients experience a DLT (i.e., 1 of 6 patients has a DLT), then enrollment at the next scheduled dose may commence.
- ≥ 2 patients within a cohort experience a DLT, then the DLT dose level will have been reached and the previous lower dose level will be considered the MTD for that dosing schedule.

Note that enrollment in the next dose cohort can begin only when the last patient enrolled in the current dose cohort completes C1 and is assessed for DLT, provided that <2 patients in the current dose cohort experienced a DLT.

Although decisions regarding dose-escalation will be made based on review of data from C1, safety data will also be collected from all patients continuing treatment and this will be reviewed periodically. Any detected cumulative toxicity may require later dose reductions or other action as appropriate, including further refinement of the MTD.

Based on evaluation of the safety and tolerability data, it may be decided that escalation to the next dose level should be more conservative than specified and that the next higher dose will be an intermediate dose level.

An MTD will be identified for each dosing schedule.

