Upon occurrence of a DLT in the first 3 patients of a given cohort dosing schedule, up to 3 additional patients will be added to that cohort dosing schedule. In the resulting 6-patient cohort dosing schedule, dose-escalation to a higher dose will occur when all 6 patients in that dosing schedule have completed the first cycle of SL-901, and no additional DLTs have occurred. If two or more DLTs occur in a given cohort dosing schedule, a DLT is established and the next lower dose level will be declared the MTD for that dosing schedule. See [Section 6.4.2](#) for DLT definition.

All dose-escalation steps and schedule recommendations will be made by a review committee, comprised of the study Investigators and Sponsor representatives, who will review the available safety and other relevant data to inform the decision on escalating to a higher dose level (see [Section 4.1.1](#)). Refer to the Data Safety Review Charter (DSRC) for further details.

“Number of Patients Planned:	For each dosing schedule, 3 to 6 patients are to be enrolled in each dose-escalation cohort in Part 1a. Up to 60 patients in total are to be enrolled in the dose-escalation cohorts. Six to 12 patients in each expansion cohort (up to 4 cohorts) are to be enrolled in Part 1b.
Diagnosis and Main Criteria for Inclusion:	Patients meeting all the following criteria will be considered eligible for study entry: 1) 18 years old or older. 2) Population by study stage: a. Part 1a: Patients with advanced, metastatic, and/or progressive solid tumors for whom there is no effective standard therapy available. b. Part 1b: Patients with histologically confirmed, advanced, metastatic, unresectable, and/or progressive solid tumors for whom there is no effective standard therapy available and their PI3K or deoxyribonucleic acid-protein kinase (DNA-PK)

pathway is deregulated or their tumor genetic profile has been shown to correlate with sensitivity to PI3K and/or DNA-PK inhibition based on clinical and preclinical experience. Specific criteria will be determined based on ongoing experiments and will be introduced in a future protocol amendment.

- 3) Evaluable or measurable disease.
- 4) Eastern Cooperative Oncology Group (ECOG) performance status ≤ 2 .
- 5) Able to take oral medications.

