4.1.1. Dose-Escalation (Part 1a)

Part 1a employs a standard 3+3 design. The SL-901 starting dose will be 20 mg on both the QD and BID schedule. The QD and BID schedules are planned to be tested in parallel, with enrollment to the current cohort for each schedule conducted on an every other patient basis. A treatment cycle is 28 days, with daily dosing throughout the cycle. The planned dose levels are summarized in [Table 5](#).

Table 5: Planned SL-901 Dose Levels in Part 1a

	Cohort						
	1	2	3	4	5	6	7
QD Dosing (mg/dose)	20	40	60	80	120	160	200
BID Dosing (mg/dose)	--	20	--	40	60	80	100
Total Daily Dose (mg/day)	20	40	60	80	120	160	200

QD = once daily, BID = twice daily

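### SAP 5.1 lets the highest tested dose be called the MTD with no failed level above it; a minor wording gap in the Protocol 6.4.1 gate should be closed too

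*Protocol*

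**What the plan says.** **MTD.** The third bullet of Protocol 6.4.1 works downward from a failed level: when 2 or more patients have a DLT, "the previous lower dose level will be considered the MTD for that dosing schedule". The synopsis does the same, starting from "If two or more DLTs occur in a given cohort dosing schedule". Protocol 4.1.2 provides for the case where no MTD is found and then refers to the maximum tested dose.

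SAP 5.1 gives a different definition: the highest level at which at most 1 of 6 subjects has a DLT in the run-in period or Cycle 1. It mentions no failed higher level. Its own Part 1b paragraph repeats the fallback to the maximum tested dose. SAP 3.1, which lists the changes from the protocol, names only the DLT population. SAP section 4 says the study stopped early and Part 1b never began.

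**Gate.** The first bullet of Protocol 6.4.1 reads: "None of these 3 patients experience a DLT in either dosing schedule, then enrollment of the next cohort may commence". The closing note opens the next cohort "provided that <2 patients in the current dose cohort experienced a DLT". Neither is limited to one schedule. The section ends: "An MTD will be identified for each dosing schedule".

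**The concern.** Identifying the MTD is the first primary objective. A reader of the report will take an MTD to be a dose with an intolerable level above it. The protocol's rule guarantees that; the SAP's sentence does not. If escalation ended for any reason other than toxicity, the SAP sentence can attach the label to the last level tested. SAP 5.1 also repeats the promise of an MTD for each schedule, which adds pressure to name one.

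The gate matters less. Table 5 gives one cohort number to a QD and a BID regimen in Cohorts 2 and 4 to 7. Without a schedule limit, the note could be read as letting DLTs on one schedule hold back the other.

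**Working it through.** **1. Compare the two MTD rules.** Take one schedule, with level k the highest level that has not failed.

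| Data | Protocol 6.4.1 and synopsis | SAP 5.1 sentence |
|---|---|---|
| Level k 1/6; next level has 2 or more patients with a DLT | MTD = k | MTD = k |
| Level k 0/6 or 1/6; next level never opened | No MTD; k is the maximum tested dose | MTD = k |
| Level k 0/3; next level never opened | No MTD; k is the maximum tested dose | Unclear, as 6 patients were not treated |

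The rules part in the second row, which an early stop makes possible. Under 3+3 a level grows to 6 only after 1 of 3 has a DLT, so 1/6 is the usual way into that row; 0/6 needs extra patients.

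**2. What 1/6 says about the DLT rate.** The one-sided 95% exact upper bound solves (1−p)^6 + 6p(1−p)^5 = 0.05. At p = 0.582 the terms are 0.418^6 = 0.0053 and 6 × 0.582 × 0.418^5 = 0.0446, which sum to 0.0499. The bound is 58%.

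**3. How easily a toxic level clears.** The documents give no true DLT rate, so these rates are assumed. P(clear) = (1−p)^3 + 3p(1−p)^5, where the first term is 0/3 and the second is 1/3 followed by 0/3.

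- p = 0.3: 0.343 + 0.151 = 0.494
- p = 0.4: 0.216 + 0.093 = 0.309
- p = 0.5: 0.125 + 0.047 = 0.172

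At 40%, then, 31% of such levels clear: 22% by 0/3 and 9% by 1/6. Only the 1/6 route literally meets the SAP's denominator.

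**4. Could escalation end with no failed level?** P(clear) is 0.973 at a true rate of 5% and 0.906 at 10%. If the rate were constant over all levels (an assumption), all 7 QD levels would clear with probability 0.973^7 = 0.83 or 0.906^7 = 0.50, from unrounded inputs. So even a full escalation need not meet a failure, and a shortened one is less likely to.

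**5. The gate.** Suppose a shared cohort has 2/3 DLTs on QD and 0/3 on BID. Counted over the whole cohort number, the note keeps the next cohort shut. Counted as in the synopsis, BID moves up. The rest of the text points to the second reading:

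- Protocol 6.4.1 starts each cohort with up to 3 patients and counts 1 of 3, then 1 of 6. A joint cohort would start with 6.
- Protocol 9.1 plans 3 to 6 patients per escalation cohort for each schedule.
- Protocol 4.1.1 has "enrollment to the current cohort for each schedule conducted on an every other patient basis".
- The second and third bullets and the last line of 6.4.1 are per schedule.

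**The case against.** On the label, the best reply is that the SAP elaborates the protocol and declares no change to the MTD rule, so the step-down rule still governs. SAP 5.1 itself separates the maximum tested dose in its Part 1b paragraph, and the SAP's index of outputs has a DLT table and listing but none that declares an MTD. All of this is true. It shows that the SAP conflicts with itself and that any wrong label would arise in the report's text. It does not settle which sentence the report's author should follow, and the only explicit definition is the one that omits the failed level. It also stands that a top level with 0/3 does not literally meet a rule stated for 6 patients, so no bound for 0/3 is relied on here.

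On the gate, a reader might infer that a QD failure closes BID. The denominators and per-schedule wording above do not support that. A reader might also infer that nothing handles BID rising past a daily dose that failed on QD. That is too strong: a review committee makes every escalation decision (Protocol 6.4.3), and 6.4.1 lets it decide that "the next higher dose will be an intermediate dose level". Operating detail is left to a charter that is not among the documents.

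**Conclusion.** The label point holds and should be corrected. As written, SAP 5.1 can name an MTD where the protocol would say none was identified. The size is conditional: 1/6 at the top level is compatible with a DLT rate up to 58%, and the 31% clearing chance rests on an assumed true rate of 40%. The documents do not say which cohorts were reached or failed, so it cannot be inferred that a dose was or will be mislabelled.

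The gate point is minor and editorial. The intent is per schedule, and the wording can no longer change the conduct of a stopped study.

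**What to change.** Replace the MTD sentence in SAP 5.1 with:

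> A dose level is called the MTD for a schedule only if a higher level on that schedule had 2 or more patients with a DLT. Otherwise report MTD not reached and give the maximum tested dose, with the number of DLTs and of DLT-evaluable patients.

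If the SAP can no longer be amended, apply the same rule in the clinical study report. It needs no new patients, visits or analyses. The price is that the report may have to say that no MTD was identified on one or both schedules.

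For any reuse of the design, limit the first bullet and the closing note of Protocol 6.4.1 to the dosing schedule concerned, as the synopsis does. This is a text change only.
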